1.1. Background and rationale

Bipolar Spectrum Disorders typically involve periods of depression, and periods of very high energy and mood (hypomania or mania). Bipolar Disorders (BDs) are common, affecting around 1 in 20 people at some point in their lifetime. They can be very distressing and disruptive to the people who experience them, and for friends and relatives. Many people with these conditions have mood issues outside depressive or manic episodes. Often these issues include ongoing low mood, and/or frequent swings in mood or emotions. These are sometimes called “inter-episode bipolar symptoms” (IEBS).

There are psychological (talking) therapies designed to help people with Bipolar Disorders, but these tend to be aimed at preventing a relapse of depression or mania, or they are aimed at helping people recover from a period of depression. There is no universally accepted talking therapy for helping people who have ongoing low mood or mood swings in between full episodes.

The aim of this study is to provide an initial evaluation of a psychological therapy designed to address these ongoing symptoms. A total of 12 people, in two consecutive cohorts of six to allow refinement of the therapy in between, will be offered the therapy and will be randomly allocated to a waiting period of 3-5 weeks after their baseline assessment. They will then repeat some of the assessment measures and commence the therapy which will be delivered over a period of approximately seven months. At the end of therapy, they will complete the set of assessment measures again and complete a three week post therapy monitoring period. Throughout the baseline, therapy and post-therapy periods they will be invited to complete some brief measures of symptoms on a weekly basis. At two points (during the first two weeks of the baseline period and of the post therapy period) they will be invited to complete a block of mood and activity monitoring when they will be asked briefly about mood and key activities five times per day for 14 days. Views on the acceptability of the therapy will be collected from participants in terms of numerical ratings of acceptability, written feedback and through interviews.

1.2. Objectives

- i) To allow initial evaluation of intervention safety, feasibility and acceptability.
- ii) To investigate whether the pattern of change in symptoms pre to post intervention is consistent with the potential of the intervention to deliver benefit.
- iii) To refine the therapy protocol and procedures for training and supervising therapists.
- iv) To develop an initial therapy competence and adherence measure.

2. Study methods

2.1. Design

Two cohort randomised multiple baseline ABA case-series design. Randomisation is to a wait period of 3,4 or 5 weeks before starting therapy. The intervention is an adapted form of behavioural therapy delivered on a one-to-one basis over up to 22 sessions, over up to 7 months.

2.2. Randomisation

Participants will be randomised to different baseline assessment lengths (between 3 and 5 weeks). The randomisation sequence will be generated and administered by an individual independent of the study on a 1:1:1 allocation sequence (block randomisation) with one block per cohort of 6. The randomisation sequence will be generated by [name] (Exeter CTU statistician) and then passed to a researcher independent of the project and research team. The research team will contact this person after eligibility is confirmed for each participant to obtain the allocation next in the sequence.

2.3. Sample Size

It is good practice to have at least 3 replications of the pattern of change across different cases (inter-case replication) as well as more than one therapist treating patients. Patients are treated in two cohorts within the current study: a total of 12 participants, 6 in each cohort, would allow these criteria to be met within each cohort (with at least two therapists seeing patients in each cohort).

Participants who exit the study after randomisation, but before completing the pre-therapy measures will be replaced (with new random allocation) to give N=12 commencing the therapy period.

2.4. Interim assessment of feasibility criteria and progression rules

Because of the intention to rapidly proceed to a feasibility trial if the therapy protocol appears promising, we will assess the data against the minimum thresholds for progression after those in cohort one have each attended at least eight therapy sessions (or have discontinued therapy, if before session 8). If the progression thresholds are met, we will apply for approval for a feasibility trial at this point. The trial preparation and approval process will take around six months; over this period learning from the remainder of the case series will continue to inform the therapy protocol. The progression rules are in place simply to ensure we do not progress with a therapy that is likely to be unsafe or unacceptable and this cannot be rectified in time prior to the trial commencing. If the progression thresholds are not met at the end of cohort one we will alter the research and therapy protocols as required (with support from the PPI panel and TSC) and progress with cohort 2. The rules will be re-examined in relation to cohort 2 (in relation to whether to proceed to a feasibility trial) once all six participants have attended at least 8 sessions or discontinued therapy.

2.4.1. Discontinuation criteria for individual participants:

1. Participant does not wish to continue with the intervention and study (participants will be considered to be remaining in the study if they discontinue therapy, unless they opt to also leave the study).
2. The participant experiences a serious adverse reaction (mental or physical health event that results in significant impairment, hospitalisation or death) that is judged to be the direct result of the intervention or trial participation.
3. Participant and / or therapy / research team believe that the intervention or trial participation will result in, or is likely to result in, a serious adverse reaction if continued.

4. The participant does not attend more than three consecutive therapy sessions without explanation despite attempts to contact them (sometimes referred to as “DNA”): this will be judged to indicate discontinuation of therapy.

2.4.2. Discontinuation of the trial:

1. Should an unexpected serious adverse reaction occur to either the therapy or the trial procedures, and this is judged to be directly related to trial participation or to the therapy, the trial will be temporarily halted pending investigation and analysis of the extent to which future risk can be mitigated against. If it is judged that this is not possible, the trial will be discontinued. This process will be led by the sponsor in collaboration with the TSC chair and CI.

2. Should information come to light that indicates that the therapy intervention or trial procedures are unsafe, the process outlined in (1) above will be followed.

2.5. Timing of final analysis

Final analysis will take place once the final data collection point has passed for the final participant and data have been entered and cleaned.

2.6. Timing of outcome assessments

Table 2.6.1: Timings of outcome assessments

Measure	Intake	Pre-treatment	Weekly*	Immediately post-treatment	7 months (30 weeks) post treatment onset	6 months (26 weeks) post end of treatment
PHQ-9	X	X	X		X	
ASRM	X	X	X		X	
Depression-elation subscale of ALS short form			X			
ALS short form	X	X			X	
Brief QoL.BD	X	X			X	
BRQ	X	X			X	
GAD-7	X	X			X	
Momentary assessment block	X			X		
Post therapy feedback questionnaire				X		

Post therapy interview				X		
Booster sessions feedback questionnaire						X

Data that are collected outside of the time-windows shown in Table 2.6.2 will be excluded from the primary analysis but included in a secondary sensitivity analysis (quantitative measures) or will be included but with discrepancy in collection time noted (qualitative).

Table 2.6.2: Time windows for data collection per assessment point

Timepoint	Data collection window	Notes
Intake (prior to randomisation)	Not applicable	Required for eligibility
Weekly from intake to 3 weeks post end of therapy (randomisation occurs between weeks 0 and 1)	+7 days	late returns within 5 days will be accepted and subsequent time point will continue as planned
5x per day for 14 days starting day after eligibility confirmed; second 14 day block starting day after end of treatment confirmed (randomisation occurs during first week of block 1)	+3 hours	late returns within this window will be accepted and subsequent timepoint will continue as planned
Pre-treatment (post randomisation)	+28 days	
7 months post pre-treatment	+28 days	
Post end of treatment	+28 days	
6 months post end of treatment	+28 days	

3. Statistical principles

3.1. Confidence intervals and p-values

In accordance with the feasibility aims of the study, all outcomes will be reported descriptively. All quantitative outcomes are continuous measures and will be reported at each timepoint measured using the mean and standard deviation. Descriptive analyses will include all reported data collected within the time window specified (Section 2.6). In addition, as a sensitivity analysis, we will also report descriptive analyses including all reported data (irrespective of whether within the time window).

In accordance with the aims of the study, which primarily concern feasibility, inferential statistical tests will be limited. Where these are carried out (calculation of pre-post change in terms of reliable and reliable and clinically significant change, and group-level, pre-post effect size), effect sizes and two-sided 95% and 90% confidence intervals will be reported.

3.2. Intervention adherence and protocol deviations

As this is a feasibility study we will not set a minimum threshold for therapy attendance in order for the participant to be considered to have had an adequate minimum dose. Instead we will explore attendance rates and present these in terms of frequencies, minimum, maximum and median. We will also consider these narratively in relation to quantitative and qualitative outcomes on a per-participant basis, in order to inform decisions about minimum adequate dose in subsequent studies of the intervention. No sensitivity analyses, i.e. by exclusion of participants who do not complete a pre-specified minimum number of sessions, will be performed.

Protocol deviations will be recorded by the study team; major deviations will be reported in terms of count and narratively in the final report.

3.3. Study populations

Analyses will use observed data only (i.e. without imputation). Data on session attendance rates will separate out any participants who left the study before the pre-treatment point and thus did not reach the point in the study where therapy commenced.

4. Trial population

4.1. Screening Data

Numbers of participants expressing an interest in the study, undertaking the initial screening process, giving consent, found to be eligible and entering the study will be reported.

4.2. Eligibility Criteria

Participants will be adults who i) meet research diagnostic criteria for Bipolar I or II Disorder, Other Specified Bipolar Disorder or Cyclothymic Disorder; ii) do not meet criteria for a manic or severe depressive episode; iii) have IEBS, defined as at least mild depressive symptoms (Patient Health Questionnaire [PHQ9] ≥ 5) or above-average bipolar mood instability defined as ≥ 1.3 on the brief Affective Lability Scale (ALS) depression-elation scale; iv) are willing to engage in psychological work addressing IEBS or its impact on functioning; v) sufficient English to complete questionnaires without translation; vi) have completed the intake measures.

Exclusion criteria include: i) current substance dependence according to ICD-11 criteria; ii) frequent and serious self-harm that cannot be safely managed in a community outpatient setting; iii) currently engaged in another psychological therapy for bipolar disorder.

4.3. Recruitment

The CONSORT diagram will include: number expressing an interest, number completing screening and reasons for any exclusion, number giving consent and assessed for eligibility, number eligible and randomised and reasons for any exclusions, number completing therapy, number giving post

therapy feedback, number completing 7 month follow up assessment, number giving feedback post booster sessions.

4.4. Withdrawal / follow-up

Withdrawal from the research aspect of the study will be reported separately to withdrawal from therapy as participants may withdraw from one but not the other. Participants who do not complete the intervention will be given the opportunity to complete the follow-ups. With respect to both, reasons for withdrawal, where available, will be reported. Numbers completing each measure at each time point will be reported.

4.5. Baseline patient characteristics

Demographic and clinical characteristics of the sample will be reported: gender, age ethnicity self-perceived financial status, psychiatric medication prescribed currently (Yes / No and numbers prescribed each type), research diagnosis (bipolar I, bipolar II, cyclothymic disorder, other specified bipolar), illness history (number of episodes, age of onset), current presenting difficulty (mood instability, low mood or both), currently held within primary care only / secondary care scores on study measures at intake. Binary and categorical characteristics will be reported as numbers and percentages in each categories; continuous characteristics will be reported using the mean and standard deviation (or median and IQR if not normally distributed), and range for age characteristics and number of previous episodes.

5. Statistical analysis

Analyses will be conducted using SPSS and STATA.

5.1. Outcome definitions

Means of assessing primary (feasibility) outcomes

1. Safety will be measured by rates of therapy-related adverse events across the study period, and rates of reliable deterioration from the pre-treatment point on the Patient Health Questionnaire (PHQ), Altman Scale for Rating Mania (ASRM), Affective Lability Scale (ALS), Generalised Anxiety Disorder questionnaire (GAD), Quality of Life in Bipolar Disorder scale (QoL.BD) and Bipolar Recovery Questionnaire (BRQ) at 7 months (30 weeks) follow-up.
2. Acceptability will be measured by therapy uptake and completion rates across the study period, and quantitative and qualitative feedback from participants and therapists at the post-therapy point.
3. Potential of the intervention to deliver benefit will be measured by rates of reliable, and reliable and clinically significant, change in the Patient Health Questionnaire and the bipolar-depression scale of the Affective Lability Scale, from the baseline period (mean score) to the 3 week post-therapy period (mean score).

Secondary outcome measures

1. Rates of reliable, and reliable and clinically significant, change on the following measures: Bipolar Disorder Recovery Questionnaire, Quality of Life in Bipolar Disorder Scale and Generalised Anxiety Disorder assessment scale from pre-therapy to 7-month follow-up.
2. Rates of reliable, and reliable and clinically significant, change on the Altman Scale for Rating Mania from the baseline period (mean score) to the 3 week post-therapy period (mean score).
3. Group-level change in PHQ, ALS, ASRM, BRQ, QoL.BD, GAD from baseline to 6-month follow-up and pre-therapy to 7-month follow-up.
4. Mood instability will be measured (in addition to the ALS) by a visual analogue scale of mood at five timepoints per day for 14 days on two occasions (pre and post therapy) for each participant. This allows for the calculation of mood instability before and after therapy.

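### The reliable-deterioration part of primary safety uses only the observed 30-week change, so it omits worsening during therapy that resolves or ends in non-response; the weekly scores are not assigned to safety

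*SAP*

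**What the plan says.** SAP section 5.1 (primary outcome 1) builds safety from two parts. The first is adverse events: "Safety will be measured by rates of therapy-related adverse events across the study period". The second is "rates of reliable deterioration from the pre-treatment point on the Patient Health Questionnaire (PHQ", followed by the ASRM, ALS, GAD and QoL.BD, and closing with "and Bipolar Recovery Questionnaire (BRQ) at 7 months (30 weeks) follow-up". Sections 5.2 and 5.3 repeat that rates of reliable deterioration will be reported and name no other time point.

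Five other places bear on this:

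- **Section 2.6.** Table 2.6.1 marks the PHQ-9, the ASRM and the ALS depression-elation subscale as weekly. Table 2.6.2 gives the span: "Weekly from intake to 3 weeks post end of therapy (randomisation occurs between weeks 0 and 1". The GAD-7, QoL.BD, BRQ and full ALS short form have no scheduled score between pre-treatment and 7 months. A 7-month score outside the 28-day window goes to a sensitivity analysis only.
- **Section 3.3.** "Analyses will use observed data only (i.e. without imputation".
- **Section 4.4.** "Participants who do not complete the intervention will be given the opportunity to complete the follow-ups". The numbers completing each measure at each time are also reported.
- **Section 2.4.** Progression is judged "after those in cohort one have each attended at least eight therapy sessions (or have discontinued therapy, if before session 8"), so that a therapy likely to be unsafe or unacceptable does not go forward. The same check is foreseen for cohort 2.
- **Section 5.2, aim (ii).** Reliable change is calculated per participant between phases. Two raters classify each weekly course as improvement, deterioration or no change, helped by baseline-corrected Tau.

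**The concern.** Section 1.1 describes a condition of depressive and manic episodes with mood swings in between. In such a condition, harm from a therapy could take the form of a worsening that comes and goes, or one after which the participant stops returning questionnaires. The deterioration rate in section 5.1 sees neither. It compares one pre-treatment score with one score at 30 weeks, about the end of a therapy lasting up to 7 months, among those who supplied both.

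The plan collects weekly scores on three mood measures over exactly this period but gives them no role in safety. The progression review, which has a stated safety purpose, normally comes well before the 30-week score. At stake is how sensitive one of the two safety components is, and whether the review in section 2.4 has any score-based safety information before it.

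**Working it through.** **Inputs.** Two cohorts of 6 (section 2.3); up to 22 sessions over up to 7 months (section 2.1), taken as 30 weeks as in Table 2.6.1; review at session 8 (section 2.4); reliable-change limit of 1.96 standard errors of the difference (section 5.2). The SAP gives no dropout rate and no episode length, so steps 3 and 4 use assumed values.

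**1. The plan's own figure.** 2 × 6 = 12 commencing therapy, which reproduces. The SAP gives no power calculation to check.

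**2. When session 8 falls.** Week of session 8 = 8/22 × therapy length in weeks.

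- 22 sessions in 22 weeks: 8/22 × 22 = week 8.0, which is 22.0 weeks before week 30.
- 22 sessions in 30 weeks: 8/22 × 30 = week 10.9, which is 19.1 weeks before week 30.

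For session 8 to coincide with week 30, sessions would have to average 30/8 = 3.75 weeks apart. The review waits for the last cohort member, so someone who started about 19 to 22 weeks or more before that person could already have a 7-month score. Hence few or no scores, rather than strictly none. By then each participant has about 8 to 11 scheduled weekly scores on each of the three weekly measures.

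**3. What one look sees.** If a worsening lasts L weeks and starts at a random time in 30 weeks, it is in progress at week 30 with probability L/30: 4/30 = 13%, 6/30 = 20%, 8/30 = 27%. This describes the 30-week look alone, not everything the plan does to detect harm.

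**4. Observed-only rate against its bounds.** With N = 12, x deteriorations seen and m scores missing, the reported rate is x/(12 − m). The true rate lies between x/12 and (x + m)/12.

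| Missing m | Seen x | Reported | Best case | Worst case |
|---|---|---|---|---|
| 2 | 0 | 0/10 = 0% | 0% | 2/12 = 16.7% |
| 2 | 1 | 1/10 = 10.0% | 8.3% | 3/12 = 25.0% |
| 3 | 0 | 0/9 = 0% | 0% | 3/12 = 25.0% |
| 3 | 1 | 1/9 = 11.1% | 8.3% | 4/12 = 33.3% |
| 4 | 0 | 0/8 = 0% | 0% | 4/12 = 33.3% |
| 4 | 1 | 1/8 = 12.5% | 8.3% | 5/12 = 41.7% |

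**5. False flags if weekly scores are used.** The limit of 1.96 leaves 2.5% on the deterioration side. Over 30 weekly scores with independent errors:

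- Flag on any single score: 1 − 0.975^30 = 53% per participant and measure.
- Flag on two consecutive scores: about 29 × 0.025² = 1.8%. Over 12 participants and 3 measures that is 36 × 0.018 = 0.65 false flags expected.

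Independence is optimistic. Weekly mood scores are likely to be correlated, and all are compared with the same baseline mean, so the real number will be higher.

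**The case against.** The strongest reply is that section 5.1 does not rest safety on deterioration alone. Adverse events related to therapy run through the whole study, section 5.2 also reports all adverse and serious adverse events, and section 5.3 has them reviewed throughout. That stands. A reader might infer that primary safety as a whole misses worsening during therapy, or has no data at session 8; the SAP does not support either reading. What remains is that the adverse-event component of the primary outcome counts only events judged therapy-related. Deterioration is the component that needs no causal judgement, and it is the one tied to week 30.

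Second, section 5.2 already looks at change between phases and has raters label deterioration. So the weekly data are not ignored. But this serves aim (ii), not safety or progression, and yields one pattern per participant. The SAP does not say how the therapy phase is scored. If by its mean, an assumed 10-point rise lasting 4 of 30 weeks would move it by only 10 × 4/30 = 1.3 points.

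Third, the SAP does not state which data feed the progression thresholds, and the protocol may. A reader might infer that the review was meant to use the 7-month rate and cannot; nothing in the SAP says so, and nothing bars the use of adverse events or weekly scores there.

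Fourth, stopping therapy is not the same as stopping response, because section 4.4 offers follow-up to non-completers. As completion numbers are reported, a reader could work out the bounds. This makes the bounds in step 4 a matter of presentation. It also means that a bias towards a safe-looking result is possible but not shown.

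Last, weekly flagging in an uncontrolled sample will pick up natural fluctuation; section 5.2 itself doubts that a stable baseline can be expected. That stands and shapes the fix.

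**Conclusion.** The point holds for the reliable-deterioration component only. That component is limited to the observed change from pre-treatment to week 30. It leaves out worsening that resolves earlier or is followed by non-response, and on the normal schedule it has few or no scores at the session-8 review. The weekly PHQ-9, ASRM and ALS depression-elation scores could fill the gap but are used only under aim (ii).

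The timing gap of 19 to 22 weeks follows from the SAP's own session count and therapy length, with sessions evenly spaced. The 13% to 27% detection figures rest on assumed episodes of 4 to 8 weeks with random onset. The bounds, such as 8% to 33% around a reported 11%, rest on assumed losses of 2 to 4 out of 12. They show the order of size and are not predictions for this study. This is an inexpensive gain in the sensitivity of a safety measure, not a fault that invalidates the plan.

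**What to change.** Keep the 7-month rate, and make these changes in sections 5.1, 5.2 and 5.3:

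- **Add a descriptive safety outcome.** For all who commenced therapy, and up to each person's last score, report the number with sustained reliable deterioration on the weekly PHQ-9, ASRM and ALS depression-elation, from session 1 to 3 weeks after therapy. One workable definition is two consecutive weekly scores beyond the reliable-change limit from the baseline-period mean. Section 5.2 defines that limit for pre-to-post change, so state the limit to be used for this comparison.
- **Make it available in time.** Give the count to date to the session-8 review alongside adverse events. No new threshold is needed for this.
- **Show the missing scores.** Report the 7-month rate with its denominator and with best-case and worst-case bounds.
- **Give a yardstick for natural variation.** Label the count descriptive, and show how often the same rule flags in the baseline period where the number of weeks allows. A wait of 3 to 5 weeks gives roughly 3 to 5 scores, hence only 2 to 4 consecutive pairs. These scores also form the mean they are compared with, so this is a rough guide.

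The cost is SAP wording and a little programming, with no new data collection. The downside is some flags from ordinary fluctuation, which the two-consecutive rule reduces but does not remove.
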